8.4.3 Withdrawal and Replacement of Subjects

8.4.3.1 Criteria for Subject Withdrawal

In accordance with the Declaration of Helsinki (Appendix 1) and other applicable regulations, a subject has the right to withdraw from the study at any time for any reason without prejudice to his or her future medical care by the physician or at the institution.

Subjects may withdraw from the study/schedule of assessments for any of the following reasons:

- Adverse Event. The patch treatment will be temporary discontinued for any subject with Grade 4 local skin reactions possibly, probably, or definitely related to the investigational product.
- A subject will be discontinued from further participation in the study for >2 grade 4 local skin reaction possibly, probably or definitely related to investigational product

- The Investigator decides that it is the subject's best interest to be withdrawn from the study.
- The subject is unwilling to continue in the study (consent withdrawal).
- Lack of compliance with protocol requirements and procedures.
- The Sponsor- Investigator or Regulatory Authorities, for any reason, stops the study.
- The subject fails to return to the clinic for scheduled visits and does not respond to telephone or written attempts at contact (lost to follow-up).
- Subject's death

The reason for withdrawal will be recorded in the clinical records and the electronic Case Report Form (eCRF) and reported annually in the IND Annual Report (21 CFR 312.33). All subjects who are withdrawn or discontinue should be provided with alternative medical care, if applicable.

8.4.3.2 Study Stopping Rules

Study enrollment will be suspended pending an expedited safety review by an independent DSMB if any of the following occur:

1. Any death related to Viaskin® dosing.
2. Any Stage 3 anaphylaxis related to Viaskin® application.
3. Marked increase in EoE symptoms with daily vomiting or severe abdominal pain in more than one patient
4. ≥ 1 SAE related to the investigational product or a study intervention
5. ≥ 2 Grade 3 AEs related to the investigational product

Upon safety review, one of the following outcomes will be determined:

- Accrual to the study may continue without modification.
- Accrual to the study may continue with modifications as prescribed by the DSMB.
- Accrual to the study should be discontinued.

All actions will be reported in compliance with local and federal regulations.

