The time of application and removal of each Viaskin® will be noted on the subject diary cards (see Section 10.10), along with any observed AE(s) (local and/or distant). Application of the Viaskin® at a similar time for each application (am or pm) is recommended.

After Visit 10, all subjects will continue treatment with open-label Viaskin® Milk 500 µg for up to 11 additional months. It is permitted at the discretion of the Investigator, to postpone the application of the first patch up to a maximum of 7 days after V10.

To increase the safety of subjects at the beginning of the open-label treatment period, in particular for subjects crossing over from placebo to the active Viaskin Milk treatment, the daily duration of application will again be adapted from Visit 10 for the first weeks of treatment: 6 hours/day during the first week, 12 hours/day during the second week, and for an entire 24 hours daily from the third week onwards. During the period of 24 hours of daily application, flexibility of 24 hours ± 4 hours of daily application is permitted.

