8.5.6 Dose Adjustments and Dose Escalation

No dose adjustments or dose escalation are planned apart from the adjustment in the duration of application during the first weeks of treatment.

Even though the subjects should ideally reach the daily 24-hour application regimen from the 15th day of patch application onwards, for subjects who may experience some severe local reactions at the initiation of the treatment, the daily duration of patch application should be adapted/reduced if necessary, to limit the severe reactions.

In case of local unbearable skin reactions or in case of systemic allergic reactions, the Viaskin® patch should be removed immediately in order to allow the reactions to subside rapidly. The next patch would be re-applied only the following day at the expected time and the reactions will be observed. If or when the local severe reactions recur, the patch can be removed at that time. This process can be repeated the following days until the time the subject can bear the patch for 24 hours a day.

If a subject is having systemic symptoms including worsening of EoE symptoms, the subject will have return for study visit and possible decrease in daily exposure to the Viaskin patch with gradually increase in exposure as tolerated.

Only one dose is being investigated in this pilot study, at the highest dose of Viaskin Milk currently under development (500 µg of cow's milk proteins) due to the limited number of subjects to be recruited.

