9.3 Visit 3: Screening; Minimum 6 weeks after Removing Milk

Subjects will have a minimum of two standard of care upper endoscopies and biopsy to confirm milk induced EoE performed, after a minimum of 6 weeks under milk-free diet and while on proton pump inhibitor. Results of the standard of care endoscopy and biopsy will be obtained by review of medical records. Research procedures at this visit include EoE Quality of life measure, and collection of any AEs. Subjects' clinical care GI and Allergy physicians will determine the order of screening standard of care endoscopies.

The following assessments/procedures will be performed:

- Physical examination (including a complete skin examination).
- Vital signs (including heart rate, blood pressure, respiratory rate, and temperature).
- Eosinophilic Esophagitis Symptom Score (see Section 11.12)
- Eosinophilic Esophagitis (Age-specific) Quality of Life Measure (Appendix 2).
- Milk-free Diet
- Diet History
- Upper endoscopy and biopsies of the esophagus (see Section 11.8) with upper endoscopy score (Appendix 2)
- Record all AEs (volunteered or in response to an open question).
- Record of all concomitant medications.

9.4 Visit 4: Eligibility/Randomization Treatment Period; Day 1

Visit 4 corresponds to the first day of treatment.

The following assessments/procedures will be performed:

- Review Pathology reports of the upper endoscopy and biopsy. Confirm eligibility by chart review of clinical records/randomize subject.
- Physical examination (including a complete skin examination).
- Vital signs (including heart rate, blood pressure, respiratory rate, and temperature).
- Eosinophilic Esophagitis Symptom Score (see Section 11.12).
- Urine pregnancy test for female of childbearing potential.
- Milk-free Diet
- Dispense diary cards (instruct subject how to complete).
- Dispense the first treatment box of investigational product to the subject.
- The investigator will take one Viaskin® patch from the box, apply the first Viaskin® to the subject, and train the subject on the proper technique and timing for applying the other patches.
- The subject will remain either in the CHOP clinic exam room or in the waiting room for at least 3 hours under observation. Patients will regularly be assessed by study staff. Should a patient experience an adverse reaction, or emergency, the patch will immediately be removed and the site cleaned. Patient will then be treated per CHOP allergy clinic emergency procedures.

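### When a stopping-rule trigger fires, section 8.4.3.2 suspends only enrolment and words every DSMB outcome as an accrual decision; nothing requires a decision on dosing of the other treated children or on open-label starts

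*Protocol*

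**What the plan says.** Section 8.4.3.2 of the Protocol lists five triggers: (1) a death related to the patch; (2) Stage 3 anaphylaxis related to it; (3) a marked rise in EoE symptoms in more than one patient; (4) at least one SAE related to the product or to a study intervention; (5) at least two related Grade 3 AEs. The consequence is: "Study enrollment will be suspended pending an expedited safety review by an independent DSMB if any of the following occur".

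The review must end in one of three outcomes. The first lets accrual go on unchanged. The second is "Accrual to the study may continue with modifications as prescribed by the DSMB". The third is "Accrual to the study should be discontinued".

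Section 8.5.1 moves all subjects to open-label active patches after Visit 10. It repeats the gradual increase in wear time, "in particular for subjects crossing over from placebo to the active Viaskin Milk treatment". The only stated leeway on the start date is investigator discretion "to postpone the application of the first patch up to a maximum of 7 days after V10".

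For the child who reacts, section 8.5.6 says that "in case of systemic allergic reactions, the Viaskin® patch should be removed immediately". Section 9.4 adds, for the observation period at Visit 4: "Should a patient experience an adverse reaction, or emergency, the patch will immediately be removed and the site cleaned".

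The SAP contains no stopping rule.

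**The concern.** The triggers describe harm from the patch or from a study procedure. Where the patch is the cause, the children at risk are those already wearing it and the placebo subjects about to receive their first active one. Suspending enrolment protects a different group, the children not yet randomized. Followed literally, the rule would bar a new child from Visit 4 while a placebo child receives a first active patch at Visit 10 during the same review.

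The Protocol calls this the first pilot study of the treatment in EoE (section 6.4.3). It enrols children from age 4, with up to 22 months of treatment each. A stopping rule is written in advance so that the first response to a serious event does not depend on someone choosing to use a general power.

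**Working it through.** The plan gives no figure on this point to reproduce. The check sets the provisions side by side and does one sum on durations.

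**1. Who is exposed.** About 22 subjects are to be randomized, 16 active and 6 placebo (16 + 6 = 22). At Visit 10 all who remain go on to open-label active patches. For the placebo subjects, about 6, that is their first exposure to milk protein by patch.

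**2. Does any provision require a dosing decision for the *other* children when a trigger fires?**

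| Protocol section | What it provides | Whom it covers | Required by a trigger? |
|---|---|---|---|
| 8.4.3.2, automatic action | Enrolment suspended | Children not yet randomized | Yes, but not about dosing |
| 8.4.3.2, outcomes | Three accrual decisions; the second allows modifications of unstated content | Accrual; possibly dosing under the second | A dosing decision is allowed, not required |
| 8.4.3.1 | Patch interrupted for a Grade 4 local reaction; withdrawal; study stop by the sponsor-investigator or regulators | The affected child, or the whole study by discretion | No |
| 8.5.1 | First open-label patch may be delayed up to 7 days | Each subject at Visit 10, by discretion | No |
| 8.5.6, 9.4 | Patch removed; exposure possibly reduced | The affected child | No |
| 8.5.10 | Unblinding at the request of the DSMB or regulator | Any subject | No; not a dosing decision |
| 12.3 | Safety assessment and reporting to IRB, FDA and safety committees | The Principal Investigator's duties | No; a reporting duty |
| 13.6.8 | DSMB may review at any time and make recommendations | Whole study | No |
| 17.2, 17.3, 17.5 | Immediate-hazard and emergency exceptions; early termination | Individual subjects or the whole study | No; discretionary |

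The last column contains no required dosing decision for the other treated children and no required decision on open-label starts.

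**3. After accrual closes.** Recruitment stops at about 22 randomized (section 8.3). The last child randomized can then receive up to 11 months of double-blind and up to 11 months of open-label patches: 11 + 11 = 22 months. During that time there is no enrolment to suspend, and outcomes about continuing or ending accrual have no object. This does not depend on how fast accrual goes.

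**4. What cannot be computed.** The accrual period is not stated, so the share of patch exposure that falls after closure cannot be derived from the documents.

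**5. What a hold would touch.** Section 8.5.8 defines non-compliance as less than 80% of medication between two visits. Between Month 3 and Month 6 the allowance is 0.20 × 3 = 0.6 months, about 18 days with a 30-day month. A longer hold would make a child non-compliant for that interval through no act of the family. Compliance below 80% is also given as an example of a deviation that excludes a subject from the per-protocol population (Protocol 13.5.3, SAP 4.1).

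**The case against.** The strongest reply is that children are far from unprotected. Every trigger forces an expedited review by an independent board. The second outcome places no limit on the modifications. The board can meet at any time and have the study unblinded for safety. The Principal Investigator must assess safety implications and notify the IRB, FDA and safety committees, and the study can be stopped at any point. Triggers 1 and 2 are made less likely by excluding active IgE-mediated milk allergy and previous severe anaphylaxis, and section 10.1 reports no systemic reactions with the patch so far. Open-label dosing restarts gradually. Leaving dosing to the board's judgement is a defensible choice, particularly for trigger 4, which can be an endoscopy event that has nothing to do with the patch.

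Much of this stands. It makes escalation likely, and it argues against an automatic hold for triggers 3 to 5. A hold also has costs for compliance and restart that must be dealt with. What remains is that none of these powers operates by default while the review is pending, and none obliges the board to rule on dosing.

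Two stronger readings are tempting. One is that a child with Stage 3 anaphylaxis goes back on a patch the next day, because section 8.5.6 says: "The next patch would be re-applied only the following day at the expected time and the reactions will be observed". The text that follows concerns recurring local reactions, and a separate paragraph handles systemic symptoms through a return visit and possible reduction of exposure. The passage mainly describes local reactions and only lacks a stated exception. The other is that most patch exposure falls after accrual closes. With no stated accrual period, that cannot be claimed.

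**Conclusion.** The concern holds as a gap in the rule and should be fixed. It reaches all of the approximately 22 randomized subjects, including about 6 who first receive active patches at Visit 10. It matters most after accrual closes, when the rule's stated actions have no object while children may still be treated for up to 22 months.

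A reader might infer that the Protocol obliges dosing to continue through a patch-related death, or that nobody could stop it. The documents do not support that: the powers exist, but they are discretionary and not tied to the triggers.

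The conclusion rests on the Protocol and SAP alone. Section 12.3 refers to a safety management plan for SAE reporting procedures, which is not among the documents. Even if that plan addresses dosing, the stopping rule in the Protocol should be complete in itself. Nothing here estimates how likely a trigger is.

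**What to change.** Amend section 8.4.3.2 to state that:

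1. the triggers apply in both treatment periods, through the last subject's Visit 17;
2. every triggered DSMB review gives three determinations: on accrual, on continued dosing of current subjects, and on open-label starts;
3. for triggers 1 and 2 only, dosing and open-label starts are held until the expedited review is complete; for triggers 3 to 5 a hold is at the DSMB's discretion.

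Supporting changes:

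- Section 8.5.1: a mandated hold overrides the 7-day limit on delaying the first open-label patch.
- Section 8.5.6: one line saying that a reaction meeting trigger 2 is not followed by re-application until the review is complete.
- Section 8.5.8, section 13.5.3 and SAP 4.1: days on a mandated hold do not count toward the 80% compliance or per-protocol rule.
- Restart: the DSMB decides whether the 6 h, 12 h, 24 h escalation is repeated.

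The cost is an amendment to wording, a few extra DSMB determinations, and possible short dosing interruptions. A hold before Visit 10 would interrupt treatment ahead of the primary endpoint. Because open-label visits are timed from Visit 10, a held start would shorten exposure before Visit 16. No new visits or data are needed.

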8.4.3.3 Evaluations at Withdrawal

For any subject who is withdrawn before completing all study visits, the Investigator should:

- Perform an end of study visit: all subjects who are withdrawn early from the trial will undergo the procedures planned for Visit 17 (see Section 9). End of study visits will be performed no later than 2 weeks after withdrawal/discontinuation.
- Complete all appropriate subject Diary and eCRF pages, providing the date and explanation for the subject's withdrawal/discontinuation.
- When indicated, arrange for appropriate follow-up and/or alternative medical care of the discontinued subject.

If the subject fails to attend for a scheduled end of study visit, there will be at least two attempts to contact the subject via telephone and written communication. If these receive no reply, the subject will be considered lost to follow-up.

8.4.3.4 Replacement of Subjects

Subjects who are withdrawn after beginning the treatment phase of the study will not be replaced. However, sufficient subjects will be included to ensure the minimum sample size (see Section 12.2).

8.5 Treatment

8.5.1 Treatments Administered

The Investigator must ensure that the investigational product will be used only in accordance with the protocol.

Following the confirmation of milk-induced Eosinophilic Esophagitis at screening, subjects will be randomized in a 3:1 ratio at Visit 4 (Day 1) into two different double-blind treatment groups to receive EPIT with Viaskin® Milk (500 µg of milk proteins) or placebo.

Repeated daily application will be made from Day 1 up to Month 9 at which time milk will be re-introduced into the diet of the subjects. The treatment will then continue during the milk re-introduction period (for 1 week to 2 months) up to the last endoscopy and biopsy. In total, the subjects can therefore receive the study treatment for up to 11 months.

Application of the Viaskin® patch will be made with progressive increase duration of application at the start of treatment: 6 hours/day during the first week, 12 hours/day during the second week, and for an entire 24 hours daily from the third week (Day 15) onwards. During the period of 24 hours of daily application, flexibility of 24 hours ± 4 hours of daily application is permitted.

For all subjects (4-17 years), the patch will be applied on each side of the spine in the inter-scapular area. The specific place where one Viaskin® is administered will represent a “Zone”. In total, six zones will be used in each subject to apply the Viaskin® : the first Viaskin® will be applied on zone 1, the second Viaskin® on zone 2 (after removal of Viaskin® 1), etc. until all six zones have been used, and the dosing will continue with zone 1, zone 2 etc.

O 1	O 4
O 2	O 5
O 3	O 6

Once applied to the skin, Tegaderm® must be used to cover the Viaskin® to prevent it from coming off. Other dressings could also be used as an alternative to Tegaderm® as allowed by the Principal Investigator.

In case the Viaskin® comes off, or after removing a Viaskin®, it is recommended that the subjects or subject's parent(s) thoroughly wipe off the zone with a moist disposable napkin or a disposable tissue and wash their hands to prevent accidental transmission of allergenic protein. If possible, the subject could take advantage of their shower time to change the Viaskin®. The previous Viaskin® is removed before the shower (or bath) and discarded, and the new one applied a few minutes after the shower (or bath) and after careful drying the skin.

The time of application and removal of each Viaskin® will be noted on the subject diary cards (see Section 10.10), along with any observed AE(s) (local and/or distant). Application of the Viaskin® at a similar time for each application (am or pm) is recommended.

After Visit 10, all subjects will continue treatment with open-label Viaskin® Milk 500 µg for up to 11 additional months. It is permitted at the discretion of the Investigator, to postpone the application of the first patch up to a maximum of 7 days after V10.

To increase the safety of subjects at the beginning of the open-label treatment period, in particular for subjects crossing over from placebo to the active Viaskin Milk treatment, the daily duration of application will again be adapted from Visit 10 for the first weeks of treatment: 6 hours/day during the first week, 12 hours/day during the second week, and for an entire 24 hours daily from the third week onwards. During the period of 24 hours of daily application, flexibility of 24 hours ± 4 hours of daily application is permitted.

8.5.2 Study Treatment Formulation

Viaskin® Milk will be administered using the Viaskin® epicutaneous delivery system. Viaskin® Milk contains a dry deposit of milk protein formulated without adjuvant. The Viaskin® is round-shaped. The inner part of the Viaskin® Milk has a diameter of 24 mm (4.5 cm² surface area). In this inner part, the milk allergen extract is deposited by electrospraying the liquid milk protein formulation, which dries instantly. The outer adhesive part of the Viaskin® is composed of a 3 mm wide band of adhesive foam to stick to the skin. The outer part of the Viaskin® Milk has a diameter of 30 mm.

The placebo treatment will consist of a similar formulation, but will be devoid of milk proteins. Once applied to the skin, the hypoallergenic adhesive film TegaDerm® must be used to cover the Viaskin® to prevent it from coming off. Other dressings could also be used as an alternative to Tegaderm® as allowed by the Principal Investigator.

AMATSI, Saint Gély du Fesc, France, will manufacture both the active and placebo Viaskin® in accordance with the requirements of Good Manufacturing Practices (GMP) and will perform the primary packaging activities (i.e. place one Viaskin® patch per pouch).

8.5.3 Study Treatment Labelling and Packaging

The secondary packaging and pharmaceutical release activities will be performed by CREAPHARM (Le Haillan, France). This manufacturer will label and package the investigational product: the containing boxes as well as each pouch will be labeled. The labeled pouches will be placed in labeled treatment boxes/kits to be delivered to subjects at each visit, with enough quantity

of Viaskin® to cover the period between two consecutive visits. The labeled and packaged investigational product will be stored according to the requirements of GMP under the storage conditions established by stability studies performed with Viaskin® Milk.

Upon reception at the clinical site, the study drug will be stored in the Investigational Pharmacy. The pharmacist will receive and store the study drug until the time of dispensing to the Investigators. Patients will return unused patches and they will be destroyed by Investigational Pharmacy. At the end of the study, the pharmacist will be responsible for destroying any unused investigational product and will provide a corresponding certificate of destruction.

8.5.4 Blinding of Study Medication

This is a randomized, double-blind, placebo-controlled study with limited access to the randomization code. Active and placebo Viaskin® will be similar in physical appearance. The treatment each subject will receive will not be disclosed to the Investigator, study center personnel, subject, Sponsor or their representatives. The treatment codes will be held according to the interactive Web response system (IWRS).

The second phase of the study will be on open-label extension with all patients receiving unblinded Active Viaskin® milk patch. There will be no blinding of study medication during this part of the study.

For details of the emergency procedure for unblinding of individual subjects, see Section 8.5.10, below.

